- a. Assessing the effect of the ONS administration on nutritional status, which includes: energy and macronutrient intake, body weight, body mass index (BMI), mid-upper arm circumference (MUAC), muscle mass.
- b. Assessing the effect of giving ONS on physical function, namely grip strength.
- c. Assess the effect of the ONS administration on the patient's inflammatory response, which includes: CRP, neutrophils, lymphocytes, neutrophil/lymphocyte ratio (NLR) and IL-6.

RESEARCH METHODS

A. Research Design

This research is an experimental study using a Double-Blinded Randomized Controlled Trial design, with the intervention group receiving ONS containing immunonutrients with a composition consisting of purple yam flour, white egg flour, whey protein, olive oil, omega-3 powder, sugar, and creamer. In contrast, the control group received a standard ONS (iso-calorie) placebo with a composition of powdered skim milk, coconut oil, sugar, maltodextrin, and creamer. Each group received two packs of ONS/day @ 57 grams, brewed into 200 ml of formula with an energy content of ± 500 kcal for three weeks.

B. Population/Subject/Sample

The population in this study were MPA patients at RSUP [name], while the research subjects were these patients who met the following inclusion and exclusion criteria.

1. Inclusion criteria
 - a. Subjects diagnosed with advanced stage MPA (stages 3 and 4) who received radiotherapy or chemoradiotherapy, both as concurrent and adjuvant therapy.
 - b. Subjects aged 18-80 years.
 - c. Can consume food through a nasogastric tube (NGT) or orally.
 - d. Willing to participate in the research by signing informed consent. However, if the patient's general condition is terrible, the family is willing to sign an informed consent and help with the research.
2. Exclusion criteria
 - a. The subject has a milk or egg allergy
 - b. Subjects with comorbid renal impairment
 - c. Subjects with poor nutritional status with $BMI < 17.0 \text{ kg/m}^2$
 - d. Subject could not stand for weighing
3. Dropout criteria:
 - a. Subject died
 - b. Subjects withdrew from the study
 - c. Average ONS consumption $< 75\%$

The size of the study subjects was determined based on parameters of protein intake because one of the significant differences in the intervention and control formulas was the protein

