content (Arnold and Richter, 1989; Dahlan, 2013). The minimum number of subjects in this study was 22 subjects, with an additional 20% of 5 subjects, so the number of research subjects in each group was 27 or 54 subjects.

C. Location and Time of Research

The location of this research will be carried out at dr. Sardjito Yogyakarta, with research time, will be carried out for 14 months, starting from March 2022 to April 2023.

D. Research Parameters

This study has several research parameters, which include nutritional status in the form of changes in body weight, BMI, MUAC, body composition (muscle mass), and albumin; handgrip strength as physical function; and inflammatory response in the form of CRP, complete blood profile (leukocytes, neutrophils, lymphocytes, neutrophil/lymphocyte ratio).

E. Materials and Procedures

1. Research Materials

Materials for the manufacture of ONS immunonutrients

- 1) Purple sweet potato flour made from purple sweet potato flour of the Antin 3 variety
- 2) Ovobel white egg flour
- 3) Whey protein isolate 90
- 4) Bertolli brand virgin olive oil
- 5) Omega-3 powder from Novotech Nutrition USA
- 6) Powdered sugar obtained from refined sand from the Gulaku brand
- 7) Fiber Creme brand creamer

Materials for making standard ONS:

- 1) Low-fat milk brand Tropicana Slim
- 2) Barco brand coconut oil
- 3) Powdered sugar obtained from refined sand from the Gulaku brand
- 4) Fiber Crème brand creamer
- 5) Maltodextrin

2. Research Procedures

a. Preparation of Intervention Substances (ONS Immunonutrient formula and standard ONS)

Making ONS formulas containing either immunonutrients or standard ONS is done by mixing all the ingredients using a mixer with the amount of each ingredient according to the predetermined amount. The main ingredient in this formula is purple sweet potato flour, made by drying fresh purple sweet potatoes which have been blanched beforehand.

b. Clinical Trials

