A clinical trial study with a double blind, randomized controlled trial design, where there was blinding on two parties, both researchers and subjects. Disguising is done on 2 types of products by assigning a specific code to each product (eg VGYJ code for standard ONS products and KMJP code for intervention ONS products), where the coding is carried out after product packaging and labeled on aluminum foil by external parties (in outside the research team) who finalized the research product. Next, make an envelope containing each of the one codes, several research subjects to be recruited, then later 1 subject will take one envelope so that it is known that the subject belongs to a group with a specific codification. The codification is only known by external parties, which will then be stored and duplicated through hard file or soft file documents to be given to the researcher after the data has been collected and statistically analyzed. Thus, the 2 types of research products (standard ONS and intervention ONS) were unknown to either the researchers or the research subjects.

c. Storage, analysis, and reporting of research data

After collecting data, the next stage is storing, analyzing and reporting research data with the following details:

- 1) The researcher collects research data and stores it in a secure place, namely a locked cupboard and in a safe place, in terms of temperature, humidity, and attack by animals such as rats. In addition, periodically (once a week) researchers will enter research data in soft files and send them to email so that there is duplication of data or documents to avoid unwanted events. Both hard and soft file data storage is carried out in a closed and locked or password manner so that subject confidentiality is maintained and safe from the reach of other parties who have no interest in research. This is done until all the data has been collected from a large number of predetermined samples.
- 2) Researchers conducted research data analysis
- 3) Researchers report research data in the form of a dissertation

d. Possible risks that the subject will experience

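### Allocation by each subject taking an envelope has no described sequence, numbering, sealing or log, so a repeated or swapped draw would leave no described record

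*Combined protocol and SAP*

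**What the plan says.** Section A (Research Design) calls the study a "Double-Blinded Randomized Controlled Trial design" and gives no method of generating the random order.

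Section E.2.b (Clinical Trials) is the only text on allocation. Parties outside the research team label the two products, for example "VGYJ code for standard ONS products and KMJP code for intervention ONS products". Envelopes are then prepared: "Next, make an envelope containing each of the one codes, several research subjects to be recruited". The natural reading is one code per envelope and as many envelopes as planned subjects. Who prepares them is not stated. Allocation follows: "then later 1 subject will take one envelope so that it is known that the subject belongs to a group".

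On records, the section says: "The codification is only known by external parties, which will then be stored and duplicated through hard file or soft file documents". This file goes to the researcher after the data have been collected and analysed. It shows which code is which product. It is not described as a list of which subject was assigned which code.

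Section B gives the planned size: "with an additional 20% of 5 subjects, so the number of research subjects in each group was 27 or 54 subjects".

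**The concern.** Random assignment is what makes the comparison of the two groups valid, and a reader should be able to check that the arm a subject received was the arm assigned. Here the record described as held outside the research team is the product key. At unblinding it can show what each code meant, but not that a given subject drew the code recorded for them. If an envelope were opened, returned and another taken, or two were exchanged, the set of envelopes would look the same and nothing in the plan would show it.

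There are only two codes, one per product, and opening the envelope discloses the code. If one product is recognised in use, the arm behind every later draw is known and the draw becomes worth steering. Section F compares pre–post differences by t-test or Mann–Whitney without covariate adjustment, so the planned analysis would not correct a prognostic imbalance produced in this way.

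**Working it through.** **1. Planned size.** 20% of 22 is 4.4, rounded up to 5. 22 + 5 = 27 per group, and 2 × 27 = 54. The stated figures reproduce, and 1:1 allocation is implied.

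**2. What is and is not described in section E.2.b.**

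| Element | In the document |
|---|---|
| Two product codes assigned externally | Yes |
| One code per envelope, one envelope per subject | Yes, by the natural reading |
| Code-to-product key held externally | Yes |
| Method of generating the order; ratio or blocking | Not described |
| Number of envelopes per code | Not described |
| Sealing, opacity, numbering, order of opening | Not described |
| Who prepares and holds the envelopes | Not described |
| Log of subject against envelope; handling of used and unused envelopes | Not described |

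**3. What the undescribed mix could mean.** If the envelopes are exactly 27:27 and all are used without redraws, the arms end 27:27. If each code were instead a simple 1:1 draw, the chance that an arm falls below the stated minimum of 22 is 2 × Σ C(54, x)/2^54 for x = 0 to 21, which is 13.4%. The document does not say which applies.

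**4. Illustration of steering.** The assumptions are not from the document: a 27+27 pool; visible prognosis correlated ρ with outcome; better-than-average subjects steered to one code and the others to the other; an unwanted draw returned and redrawn once with probability f.

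- Unwanted draws occur about half the time, so redraws per trial ≈ 54 × 0.5 × f = 27f.
- With codes near 50:50, P(wanted code) ≈ 0.5 + 0.5 × f × 0.5. This is 0.55 at f = 0.2 and 0.575 at f = 0.3. If every unwanted draw were redrawn (f = 1), it would be 0.75.
- Prognosis differs between arms by about √(2/π) × f = 0.798f SD, so outcome bias ≈ 0.798 × ρ × f.
- Standard error of the difference = √(2/27) = 0.272 SD. Type I error ≈ Φ(−1.96 + bias/0.272) + Φ(−1.96 − bias/0.272).

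The simulated columns are from 40,000 trials per scenario with the pool drawn without replacement and a two-sided 5% t-test.

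| f | ρ | Redraws | Bias, formula | Bias, simulated | Type I, formula | Type I, simulated |
|---|---|---|---|---|---|---|
| 0.2 | 0.3 | 5.4 | 0.048 | 0.046 | 5.4% | 5.1% |
| 0.3 | 0.3 | 8.1 | 0.072 | 0.064 | 5.8% | 5.6% |
| 0.2 | 0.5 | 5.4 | 0.080 | 0.078 | 6.0% | 5.8% |
| 0.3 | 0.5 | 8.1 | 0.120 | 0.112 | 7.2% | 7.0% |

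The formula runs slightly high because the pool runs down. Quoted ranges are rounded to allow for simulation error.

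**5. Code not recognised.** The preferred code is then unrelated to treatment, so the shift is equally likely to favour either arm. Simulated mean bias is within 0.001 SD of zero in all four scenarios. Type I error is 5.3%, 5.7%, 5.9% and 7.0%, the same as above apart from simulation error, because a two-sided test responds to a shift in either direction.

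**The case against.** The strongest reply is that silence is not evidence of a bad procedure. The text does not exclude an ordered stack, does not say who prepares or holds the envelopes, and does not say that assignments go unrecorded. Section E.2.c describes weekly data entry with duplicate copies. Taking well-mixed, identical, sealed envelopes without replacement is a valid random mechanism. The product key stays with outside parties until after analysis, so someone tempted to redraw would not be told which code is the intervention.

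Most of this stands. A reader might infer that the allocation is non-random, that no sequence exists, or that the external party has no part in the draw. The document supports none of these; it only fails to describe the safeguards. A reader might also infer that a handful of redraws could decide the result. The figures do not support that: about five redraws move the estimate by roughly 0.05–0.08 SD against a standard error of 0.27 SD. The redraw rates and correlations are assumptions, and visible prognosis may correlate only weakly with a pre–post difference.

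What does not stand is the idea that coding closes the gap. Without recognition, mean bias vanishes but consistent steering still inflates type I error. Recognition is also conceivable: one product is based on purple sweet potato flour and the other on skim milk, and no matching is described. The document does not describe how either looks, so this is a possible route and not a finding that blinding fails. General data storage is also not an envelope log.

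**Conclusion.** The point holds as a weakness in concealment and audit trail. The plan states a method of allocation but describes nothing that would show a repeated or swapped draw, and the only externally held record it describes is the product key.

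The size is modest and conditional. With assumed redraw rates of 20–30% and a recognised code, bias is about 0.04–0.07 SD at correlation 0.3 and 0.08–0.11 SD at 0.5. Without recognition, mean bias is about zero. Type I error is about 5.5–7% either way, nearer 5–6% at correlation 0.3. The true redraw rate may be zero; the difficulty is that no record described in the plan could establish it. This is a cheap improvement worth making, not a defect that invalidates the design.

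**What to change.** Replace the draw in section E.2.b with the following:

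- The external party generates a computer-randomised 1:1 order of the 54 codes, seals each in an opaque envelope numbered 1 to 54, and keeps the list.
- After consent and baseline measurements, the subject identifier, date and time are written on the next envelope in order before it is opened.
- At the end, used and unused envelopes are reconciled with the list and mismatches are reported.

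A fixed 27:27 list also settles the undescribed mix of envelopes. It does not remove the two-code weakness, but writing the details before opening means that a redraw would show in the reconciliation.

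The cost is a list, numbered envelopes and slightly more paperwork, using the external party already in place. No extra patients or procedures are needed. Subjects would no longer draw for themselves. If equivalent safeguards are already used in practice, describing them in section E.2.b resolves the point.

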For the measurement of research parameters in the form of nutritional status, it relatively does not pose a medical risk or trauma to the subject; while taking blood samples there is a risk in the form of phlebitis but this can be prevented by handling blood sampling, by a competent laboratory assistant. The product consumed by the subject was in the form of ONS or liquid food (such as milk) dense in nutrition (high in energy, high in protein, containing immunonutrients in the form of anthocyanin and omega 3), which was recommended by ESPEN as nutritional support for cancer patients undergoing radiotherapy. In addition, the consumption of products provided in the form of standard ONS or those containing immunonutrients carries a risk of digestive tract disorders, such as diarrhea, bloating, or constipation. If this happens, the subject will be referred to the doctor in charge of the study (DPJP or a radiation oncologist/dr. Sp. Onk. Rad) for examination and medication, the handling costs are the full responsibility of the researcher

F. Design of Data Processing/Analysis

The research data results were analyzed descriptively in the form of average \pm standard deviation if the data were normally distributed or median if the data were not normally distributed. The pre and post-test dependent variable data in each treatment and control group will be analyzed using a paired t-test if the data is normally distributed. Still, if the data is not normally distributed, it will be analyzed using Wilcoxon. As for the analysis of the difference between the pre and post test data then comparison between the control and intervention groups was carried out with the Independent t-test if the data was normally distributed, but if it was not normal, then it was analyzed using Mann Whitney.

G. Research Ethics

This research has received permission for ethical research feasibility from the Health Research Ethics Commission, Faculty of Medicine, Public Health and Nursing, Universitas Gadjah Mada Yogyakarta Indonesia with the number KE/FK/0996/EC/2021. Then before participating in the research, there will first be an explanation of the research's aims and objectives, the course of the research, and the benefits and risks that prospective research subjects may face. If the subject understands and agrees to participate in the study, the subject is asked to sign the informed consent that has been provided.

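### Diarrhoea, bloating and constipation are foreseen with both products, but the plan does not provide for recording them, reporting them by arm, or recording why consumption falls below 75%

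*Combined protocol and SAP*

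**What the plan says.** Section E.2.d of the protocol (possible risks) covers both arms. It speaks of the "consumption of products provided in the form of standard ONS or those containing immunonutrients" and says that this "carries a risk of digestive tract disorders, such as diarrhea, bloating, or constipation". The consequence given is clinical: "If this happens, the subject will be referred to the doctor in charge of the study", with examination, medication and costs covered. The section does not mention recording, grading, counting or comparing the events.

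The planned measurements appear in two places:

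- The specific goals (Introduction, C.2) list "energy and macronutrient intake, body weight, body mass index (BMI), mid-upper arm circumference (MUAC), muscle mass", then grip strength and inflammatory markers including IL-6.
- Section D (Research Parameters) lists "nutritional status in the form of changes in body weight, BMI, MUAC, body composition (muscle mass), and albumin", followed by "handgrip strength as physical function; and inflammatory response in the form of CRP, complete blood profile" with its components.

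Section B.3 makes average ONS consumption below 75% a dropout criterion, alongside death and withdrawal. Section F plans paired and independent t-tests, with Wilcoxon and Mann-Whitney as alternatives, on pre and post values and their differences.

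**The concern.** The plan foresees a harm of the products under test and does not say that it will be written down. Symptoms over a three-week intervention cannot be reliably reconstructed afterwards, so an analyst could not repair the omission later.

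Two things are at stake. The first is harms reporting. These patients are also receiving radiotherapy or chemoradiotherapy, so a single case of diarrhoea can rarely be attributed to the product. A count by randomised arm is the interpretable comparison.

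The second is the 75% rule. A patient who drinks less because of bloating or diarrhoea could become a dropout under B.3. Without recorded reasons, nobody could tell whether such losses were due to intolerance or whether they fell more heavily on one arm.

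**Working it through.** **Step 1: look for the events wherever they could be planned.**

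| Place in the protocol | Content | Gastrointestinal event? |
|---|---|---|
| C.2 Specific goals | intake, weight, BMI, MUAC, muscle mass, grip strength, CRP, neutrophils, lymphocytes, NLR, IL-6 | none |
| D Research Parameters | weight, BMI, MUAC, muscle mass, albumin, handgrip, CRP, leukocytes, neutrophils, lymphocytes, NLR (11 items) | none |
| B.3 Dropout criteria | death, withdrawal, consumption below 75% | none; no reason asked for |
| E.2.c Data storage and reporting | storage, analysis, dissertation | none |
| E.2.d Possible risks | three symptoms named, referral | named, no recording stated |
| F Data analysis | tests on pre and post values and differences | no method for counts or proportions |

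Section D alone is not the full list, since C.2 adds intake and IL-6. The gap remains when the two lists are combined.

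**Step 2: the plan's own sample size.** Section B gives a minimum of 22, plus 20%. 22 × 0.20 = 4.4, rounded up to 5; 22 + 5 = 27 per group; 2 × 27 = 54. This reproduces. The 22 cannot be checked, because no difference, SD, alpha or power is given. The addition is 5 of 27 patients per arm. The plan does not say what it is for; I take it to be an allowance for losses.

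**Step 3: what a comparison by arm could show.** The documents give no event rates, so those below are assumptions, with two-sided alpha 0.05. The approximate power is

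Φ{(|p2 − p1| − 1.96·√[2p̄(1−p̄)/n]) / √[(p1(1−p1) + p2(1−p2))/n]}, where p̄ is the mean of p1 and p2.

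For 10% against 50% at n = 27: p̄ = 0.30; √(2 × 0.21/27) = 0.1247; √[(0.09 + 0.25)/27] = 0.1122; (0.40 − 1.96 × 0.1247)/0.1122 = 1.39, so power is 92%. Fisher's exact test, summed over all possible tables, gives 87%.

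| Assumed rates | n = 27: approx. / exact | n = 22: approx. / exact |
|---|---|---|
| 10% vs 30% | 45% / 31% | 38% / 28% |
| 20% vs 40% | 36% / 26% | 30% / 21% |
| 10% vs 40% | 73% / 63% | 64% / 55% |
| 10% vs 50% | 92% / 87% | 85% / 79% |

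The half-width of the 95% CI for the difference, at an equal true rate p, is 1.96·√[2p(1−p)/n]. At n = 27 it is 1.96·√(0.18/27) = 16 points for p = 10% and 1.96·√(0.42/27) = 24 points for p = 30%. At n = 22 it is 18 and 27 points.

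A descriptive table with an interval is realistic; a powered test is not.

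**The case against.** **Silence is not proof that nothing will be recorded.** Affected patients are referred and the researcher pays, so the researcher would learn of at least some events. This stands as a limit on wording: the documents support saying that no recording or reporting by arm is specified, and no more. It does not close the gap, because referral captures only the cases that come forward.

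**Unequal intolerance is a conjecture.** Section E.2.d names the same risks for both products without distinction, both contain sugar and the same creamer, and patients with milk or egg allergy are excluded. The documents contain no tolerability data and do not say that symptoms lower intake. This stands. Different symptom rates in the two arms, and an effect on consumption, are possibilities only.

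**The efficacy comparison is not shown to be wrong.** A reader might infer that, without symptom data, the trial cannot separate an effect of composition from an effect of intolerance, and so cannot trust a difference in intake or weight. The documents do not support this. Intake is itself a stated outcome and would be compared. Intolerance caused by a product is part of that product's effect and already lies within the randomised comparison; a table of symptoms would not split the two.

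**The 75% rule is a separate matter.** If dropping low consumers selects the patients who are analysed, a checklist does not undo that. This also stands. Recorded reasons can make such selection visible, but they cannot remove it.

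**Conclusion.** The point holds as a gap in harms recording and reporting. The plan names three gastrointestinal risks of both products, and no objective, parameter or analysis captures them. It also does not plan to record why consumption falls below 75%. As written, the trial could not report this harm by arm, nor show whether losses under the 75% rule are related to intolerance and unequal between arms.

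Its reach is limited. It does not by itself invalidate the efficacy comparison. With 27 per arm, roughly 10% against 50% would be needed for power above 80%, and smaller differences would usually be missed. Those rates are assumed, and the calculation takes all 27 per arm as counted. The omission itself rests on the text and on no assumed figure. It is worth correcting because the remedy is cheap and the data cannot be recovered later.

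**What to change.** - Add to section D a short fixed checklist of diarrhoea, bloating and constipation, with the worst severity over the three weeks. Ask it in the same way in both arms while patients and staff are blinded to the product codes.
- Add to section F a descriptive table by arm: number and proportion of patients with each symptom, and the difference with its 95% CI, for all randomised patients who took any ONS, including those below 75%.
- Record the reason whenever average consumption falls below 75%, and tabulate the reasons by arm.
- State that these comparisons are descriptive and not powered.

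The cost is a few minutes of data collection per contact and one extra table. The 75% rule implies that consumption is recorded somehow, but the protocol describes no form or contact schedule, so the frequency of the checklist must be stated as well. Nothing here alters the products, their amounts, the handling of symptoms or the 75% rule.

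### No outcome is named primary, and section F tests every outcome alike with no significance level, hierarchy or multiplicity rule

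*Combined protocol and SAP*

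**What the plan says.** The specific goals (Introduction, C.2) list, for nutritional status, "energy and macronutrient intake, body weight, body mass index (BMI), mid-upper arm circumference (MUAC), muscle mass". They add grip strength for physical function and, for inflammation, "CRP, neutrophils, lymphocytes, neutrophil/lymphocyte ratio (NLR) and IL-6". None is ranked above another.

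Section D (Research Parameters) gives a second list. It opens "This study has several research parameters, which include nutritional status in the form of changes in body weight, BMI, MUAC", continues with muscle mass, albumin and handgrip strength, and ends with "inflammatory response in the form of CRP, complete blood profile (leukocytes, neutrophils, lymphocytes, neutrophil/lymphocyte ratio". Intake and IL-6 appear only in C.2; albumin and leukocytes appear only in section D.

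Section F applies the same rule to all of them. Within each arm there is a paired t-test or Wilcoxon test. For the pre-post differences, "comparison between the control and intervention groups was carried out with the Independent t-test if the data was normally distributed", with Mann-Whitney otherwise. No significance level, hierarchy or multiplicity method is stated.

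On sizing, section B says "The size of the study subjects was determined based on parameters of protein intake", because the two formulas differ in protein content. It then says "The minimum number of subjects in this study was 22 subjects", raised to 27 per group and 54 in total.

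**The concern.** A trial that asks whether a product affects nutritional status and inflammatory response needs to say in advance which comparison answers the question. Here about a dozen comparisons stand on an equal footing. If one of them reaches significance, nothing in the plan stops it being presented as the main finding, and a reader could not tell a planned result from one picked afterwards.

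The coding procedure in section E.2.b helps only in part. The product code stays closed until the data have been analysed, so the researchers cannot choose a result because it favours the intervention. They do see every coded p-value, and so could still choose by significance.

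The sample size does not settle the matter. Protein intake is the only variable used for sizing, but the plan does not call it primary, and an arm difference in it partly reflects what was supplied rather than how patients responded.

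**Working it through.** **The plan's own figure.** 20% of 22 is 4.4, rounded up to 5; 22 + 5 = 27 per group; 2 × 27 = 54. This matches section B. The starting 22 cannot be reproduced, because no difference, SD, significance level or power is given.

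**Count of outcomes.**
- Section D: body weight, BMI, MUAC, muscle mass, albumin, grip, CRP, leukocytes, neutrophils, lymphocytes, neutrophil/lymphocyte ratio (NLR) = 11.
- C.2: 12 if macronutrients count once, 14 if they count as three.

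The error rates below use the 11 in section D. Intake is left out because the products themselves may shift it. Section F's within-arm tests are not counted.

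**Assumptions.** Two-sided 0.05 per test (the plan gives none), no true effects, 22 per group.

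**Step 1: the naive ceiling.** If all 11 were independent, the chance of at least one false difference would be 1 − 0.95^11 = 43.1%. For at least one in a given favourable direction it would be 1 − 0.975^11 = 24.3%. These cannot be the real figures. BMI change is weight change rescaled by height, NLR is computed from neutrophils and lymphocytes, and leukocytes are largely the sum of those two.

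**Step 2: remove the overlap.** Dropping those three leaves 8 outcomes. Under independence, 1 − 0.95^8 = 33.7% and 1 − 0.975^8 = 18.3%.

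**Step 3: keep all 11 but build the three from their parts.** This was done by simulating t-tests at 22 per group, with assumed height SD 0.08 m and neutrophil-change SD three times the lymphocyte-change SD.

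| Common correlation of the other outcomes | At least one false difference | At least one falsely favouring the ONS |
|---|---|---|
| 0 | about 36% | about 20% |
| 0.7 | about 20–21% | about 10–11% |
| Single test | 5% | 2.5% |

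The last column also assumes a favourable direction for each outcome, which the plan does not give. Its ratio to a single test runs from 10/2.5 = 4 to 20/2.5 = 8.

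**Protein supplied.** Two packs of 57 g at 15.8 g per 100 g give 2 × 57 × 0.158 = 18.0 g/day in the intervention arm. The control product's protein content is not stated, so the arm difference built into the products cannot be computed.

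**What 22 per group means for another outcome.** At an assumed 80% power and two-sided 5%, the normal approximation gives d = √(2/22) × (1.960 + 0.842) = 0.845 SD. The t-test calculation gives 0.865, so about 0.86 SD.

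**The case against.** The strongest reply is that protein intake is the lead variable in all but name. It falls under goal (a) as macronutrient intake, it is the variable used for sizing, and section B gives a reason for choosing it. That is a fair reading, and it means protein intake is not foreign to the plan. But the plan never says so, the general objective concerns nutritional status and inflammatory response, and naming protein intake as lead would still leave every other outcome tested without a hierarchy.

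Several further points stand and limit the claim:
- Section D says its parameters include those listed, so it is not a closed list. Leaving out intake and IL-6 does not show that they were dropped.
- The plan permits picking a main result; it does not instruct it. Its stated purpose is to identify and analyse effects, and the results go into a dissertation.
- A reader might infer that a null result would be uninterpretable. It would not be: with a planned n and reported means and SDs, an interval can be formed. What is missing is a target difference to read it against.
- Outcomes are correlated and some are derived from others, so the independence figures overstate the risk.

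The plan does not call itself exploratory. It describes a double-blinded randomised trial of effectiveness. If exploratory is what is meant, saying so is an acceptable repair.

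**Conclusion.** The point holds and should be fixed before analysis. No comparison is designated as the main one, and one unadjusted rule covers all outcomes. Under the stated assumptions the chance of at least one false between-group difference is about 20–36%, that is 4 to 7 times the 5% of a single test (20/5 = 4; 36/5 = 7.2). If favourable directions are also assumed, the chance of at least one falsely favouring the ONS is about 10–20%, or 4 to 8 times 2.5%.

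Two stronger readings are not supported. A reader might quote 43%, 24% or a tenfold inflation, but those need 11 independent outcomes, which section D's list rules out. A reader might also conclude that the sample size is wrong. Nothing shows that: 22 per group was derived for protein intake from inputs that are not stated, and it carries no stated assurance for any other outcome.

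**What to change.** Before any group comparison is run, even by product code:

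1. Name one between-group comparison, with its time point, as primary at two-sided 5%, using section F's test. The sponsor chooses the outcome; change in body weight from baseline to the end of the three weeks is one example.
2. Either test the other outcomes by Holm only if the primary is significant, or label them all exploratory. The gate matters. With nine secondaries tested by Holm and no gate, the overall error under independence is 1 − 0.95 × (1 − 0.05/9)^9 = 9.65%; with the gate it is 5%.
3. Do not count BMI as evidence separate from weight.
4. State that 22 per group was derived for protein intake only and corresponds to about 0.86 SD on another outcome at an assumed 80% power and two-sided 5%. If that is implausible for the chosen primary, call the trial exploratory for it.

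As a secondary clean-up, reconcile section D with C.2.

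**Cost.** This is a text amendment if the primary is a section D outcome and section F's test and the planned analysis set are kept. No re-sizing is asked for. It costs more if the primary is analysed in all randomised patients. Week-3 data would then be needed after death, withdrawal or the dropout rule based on "Average ONS consumption", together with a missing-data rule. Keeping intake and IL-6 in the single list may need dietary records and assays if these are not already planned.

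**Downside.** Fewer outcomes can be claimed as confirmed, and none if the primary fails. With nine secondaries (11 less BMI and the primary), Holm's first step is 0.05/9 = 0.0056, which needs about 1.14 SD at 22 per group for 80% power.
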